Aborted Procedure: Failed completion of the assigned treatment where the subject was prepped for the index procedure, but the device did not enter the vasculature or surgical stripping was not initiated for any target vein.	Follow subject for 30 days from the date of the attempted index procedure for AE assessment only, which can be completed as a phone call visit if deemed appropriate by the treating physician. Any data collected prior to and during the attempted index procedure, including AE and device deficiency, should be reported on applicable CRFs.
No Procedure (CEAP 2-5): Subject is randomized (considered enrolled) but withdraws from the study after randomization without any attempt to conduct the procedure (e.g., COVID-19 exclusion, subject withdrawal, etc.).	Subject will not be followed in the study for any duration and can exit the study. Complete Study Exit CRF.
Randomization Procedure Not Followed (CEAP 2-5; major protocol deviation): Subject treated with a modality they were not randomized to.	Follow subject schedule per schedule of events and data collection in section 10.1. Report protocol deviation as "randomization procedure not followed".

[figure not shown]

Figure 3: Flow-Diagram from Subject Screening to Follow-up

Medtronic Business Restricted

CONFIDENTIAL

056-F275, v B Clinical Investigation Plan Template

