7.1.3 Analysis Sets

CEAP 2-5 randomized studies

The primary analysis set for Randomized Studies will be the ITT analysis set. Per-protocol (PP) analyses may be performed as a sensitivity analysis. All analysis sets have been defined with the intent of minimizing bias in the data analysis.

Intent-to-Treat (ITT): All patients who are randomized in the arms in each study will be included in the analysis regardless of the treatment received or the outcome of the treatment.

Per-Protocol (PP): The ITT population excluding failed and no procedure treatment outcomes, subjects that are treated with the modality they were not randomized to and/or have not met the inclusion/exclusion criteria. A failed procedure with no procedure treatment outcomes is defined as a procedure where the procedure treatment was never attempted or a procedure that was aborted.

As treated (AT): Includes subjects in the arm they are treated with according to the treatment actually received, regardless of the arm they were randomized to.

VLU (single arm) Study

Intention-to-Treat (ITT): All patients with CEAP 6 who are enrolled in this study (either successful, incomplete or failed treatment outcome) will be counted in the ITT population, which will be the primary analysis set.

Per-Protocol (PP): The ITT population excluding failed treatment outcome and/or subjects that have not met the inclusion/exclusion criteria. A failed procedure with no procedure treatment outcomes is defined as a procedure where the procedure treatment was never attempted or a procedure that was aborted.

The primary analysis for this CEAP 6 single arm study will be on intention-to-treat (ITT) population. All analysis sets have been defined with the intent of minimizing bias in the data analysis.

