7.9.1.1.5 Determination of Subjects' Data for Analysis

ITT population with available data will be used for the primary analysis on primary endpoints. For the sensitivity analyses, PP and AT populations will be used on primary endpoints.

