7.9.1.2.5 Determination of Subjects' Data for Analysis

The return to work analysis will consist of patients in the ITT population who report having an occupation (employed or independent worker, including stay-at-home parent) at their baseline visit. The anatomic closure analysis will consist of the ITT population with available data will be used for the primary analysis on key secondary endpoints. For a sensitivity analysis, AT and PP populations will be used on key secondary endpoints.

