The probability of target vein closures of any target vein at each time point will be summarized by treatment arm in each study. The probability for each treatment arm will be estimated using the Kaplan-Meier method. Day zero is the date of the index procedure. The censoring time is the time to last study visit (scheduled or unscheduled), the time point for analysis, or time to exit, whichever comes first.

Determination of Subjects for Analysis

The anatomic closure analysis will consist of the ITT population.

3. Technical success of each target vein immediately post-index procedure

Hypothesis

The following hypothesis will be tested:

$$H_0: \pi_A = \pi_C$$

$$H_a: \pi_A \neq \pi_C$$

Where π_A and π_C are the percentage of technical success post-index procedure in the VenaSeal™ system arm and the ETA or surgical stripping arm, respectively.

Endpoint Definition

- For subjects treated with VenaSeal™ system or ETA this is defined as DUS showing vein closure along the entire treated vein segment with no discrete segments of patency exceeding 5 cm.
- For subjects treated with surgical stripping this is defined as the absence of clinically significant remnant refluxing truncal vein incompetency and no discrete segments of patency exceeding 5 cm.

Analysis Methods

The percentage of technical successes will be summarized by treatment arm in each study. The numerator is the number of technical successes, the denominator is the number of target veins treated at the index procedure. Fisher's Exact test will be used to compare arms for the endpoint.

Determination of Subjects for Analysis

The technical success analysis will consist of the AT population.

4. Reintervention of any target vein (including primary target vein) through 60 months, assessed at each follow-up visit. Subjects enrolled in the VenaSeal vs. Surgical Stripping Study will be followed through the 12 months visit only.

Hypothesis

The following hypothesis will be tested:

$H_0: r_A = r_C$

$H_a: r_A \neq r_C$

Where r_A and r_C are the rates of reintervention in the VenaSeal™ system arm and the ETA or surgical stripping arm, respectively.

Endpoint Definition

A reintervention is a retreatment of any segment of any target vein in the target limb previously treated as part of the study at the index procedure.

Analysis Methods

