7.9.1.5 Safety secondary endpoints

1. Adverse events (AEs) occurring in the target limb, evaluated from index procedure through 12 months.

Hypothesis

There is no formal hypothesis test for this study objective.

Endpoint Definition

Adverse events occurring in the target limb defined as any of the following:

- Hypersensitivity to VenaSeal™ adhesive, defined as an allergic reaction to the VenaSeal™ adhesive. The presence of hypersensitivity is confirmed through adjudication. Relatedness to a study procedure and relatedness to the study device are defined.
- Phlebitis, defined as inflammatory reaction of a treated vein. The presence of phlebitis is confirmed through adjudication. Relatedness to a study procedure and relatedness to the study device are defined.
- Granuloma, defined as a grouping of macrophages. The presence of granuloma is confirmed through adjudication. Relatedness to a study procedure and relatedness to the study device are defined.
- Endovenous glue induced thrombosis (EGIT) or endovenous heat induced thrombosis (EHIT) for VenaSeal or Thermal Ablation, defined as extensions of a thrombus that extend from the treated vein into the deep venous system. The presence of a glue extension, thrombus extension, or combination glue/thrombus is confirmed through DUS visualization of the extension into the common femoral vein or popliteal vein from the target vein and extension length is specified.

CEC determination of the above events will be used for reporting.

Analysis Methods

Adverse events that are in any of the above enumerated categories will be characterized. Adverse events will be categorized per the specified definitions, and then summarized by study group.

Determination of Subjects for Analysis

The safety analysis will consist of the ITT population.

2. Additional events evaluated through 12 months:

- Symptomatic deep vein thrombosis (DVT) events

- Symptomatic Pulmonary embolism (PE)
- Serious adverse events (SAEs)

Hypothesis

There is no formal hypothesis test for this study objective.

Endpoint Definition

CEC determination of serious adverse events will be used for reporting. The MedDRA codes for Deep vein thrombosis and Pulmonary embolism will be used for reporting of DVT and PE adverse events.

Analysis Methods

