7.10 Safety Evaluation

Descriptive statistics for the safety events will be provided. Quantitative variables will be presented with mean and standard deviation or median, minimum and maximum as appropriate. Qualitative variables will be presented with frequency and percentage. AEs will be tabulated and reported using the current version of MedDRA dictionary. SAEs will be tabulated and reported up to 60 months (up to 12 months for VenaSeal vs. Surgical Stripping study).

All observed device deficiencies that could have led to a serious adverse device effect and deaths with reason will be listed. Patient data listings and tabular and graphical presentations of results will be provided if needed.

Counts of Adverse Events through 60 months will be calculated for each study arm within each study, by event severity, by event type, by event relatedness to the study procedure, and by relatedness to the study device. Adverse events through 60 months will be summarized by treatment, System Organ Class (SOC) and Preferred Term (PT) terms on ITT. Similar counts will be provided up to 12 months in the VenaSeal vs. Surgical Stripping study.

A summary listing of all adverse events, including severity, treatment needed, resolution, relatedness to the study procedure, and relatedness to the study device will be produced.

A summary listing of all observed device deficiencies that could have led to a serious adverse event will be produced.

A summary listing of all deaths, including reasons for each death, will be produced.

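### Randomised-study safety is summarised only on ITT, which keeps untreated, unfollowed subjects in the crude SAE denominator and tabulates wrong-modality events under the randomised arm

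*SAP*

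**What the plan says.** SAP 7.9.1.5 gives the same set for target-limb AEs and for DVT, PE and SAEs: "The safety analysis will consist of the ITT population". SAP 7.10 repeats the choice for the general tables: "Adverse events through 60 months will be summarized by treatment, System Organ Class (SOC) and Preferred Term (PT) terms on ITT". SAP 7.1.3 defines ITT for the randomised studies: "All patients who are randomized in the arms in each study will be included in the analysis regardless of the treatment received". SAP 6.1 adds that each subject is analysed in the randomised arm.

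The same section defines an as-treated (AT) set: "Includes subjects in the arm they are treated with according to the treatment actually received". It is the main set in one place, SAP 7.9.1.4: "The technical success analysis will consist of the AT population". It is a sensitivity set in two others, SAP 7.9.1.1.5 ("For the sensitivity analyses, PP and AT populations will be used on primary endpoints") and SAP 7.9.1.2.5 ("For a sensitivity analysis, AT and PP populations will be used on key secondary endpoints"). No safety analysis is assigned to it. The pain endpoint in SAP 7.9.1.7 is already limited to randomised subjects who had a procedure.

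The protocol's follow-up rules differ by treatment outcome (section 9.2, Table 5):
- No Procedure: "Subject will not be followed in the study for any duration and can exit the study".
- Aborted procedure: 30 days, for AE assessment only.
- Treated with the other modality: the full schedule.

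Protocol sections 10.9 and 12.3 start AE reporting when the index procedure is initiated.

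**The concern.** Safety depends on exposure, so the analysis set should follow exposure. ITT departs from it in two ways.

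1. **Untreated subjects.** A randomised subject who never has a procedure is in the safety set but cannot have a reportable AE. That lowers any percentage that uses the ITT number. It also leaves the Kaplan-Meier SAE analysis with no starting date for that subject, and the SAP gives no rule for this.
2. **Wrong-modality subjects.** Their events are counted in the randomised arm. An adhesive hypersensitivity in a subject randomised to ETA but treated with VenaSeal would appear in the ETA column. An EHIT in the reverse case would appear under VenaSeal.

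The plan foresees both kinds of subject: Table 5 names them and the per-protocol definition removes them. Randomisation precedes collection of baseline data and may take place at screening (protocol 10.4). Allocation is open, and the protocol notes that procedures may differ in cost to the patient (section 6). Unequal withdrawal after allocation is therefore plausible, although neither document gives a rate. At stake are the descriptive safety rates by which readers will compare the treatments.

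**Working it through.** **Which statistics are affected (SAP 7.9.1.5 and 7.10)**

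| Statistic | Stated denominator or origin | Effect of ITT |
|---|---|---|
| Crude SAE proportion to 12 months | all target limbs or subjects | diluted by untreated subjects; crossovers placed by randomised arm |
| Kaplan-Meier SAE probability | day zero is the index procedure | no day zero if untreated, and no rule given; crossovers by randomised arm |
| DVT and PE | numbers of events and patients | crossovers by randomised arm; no denominator stated |
| Target-limb AEs | summary by study group | crossovers by randomised arm; diluted only if percentages use the ITT number |
| AE tables in 7.10 | on ITT | same; 7.10 and 7.2 call for percentages in general terms |

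**Inputs.** The documents state no figure for the safety set, so there is none to reproduce. Planned sizes are 264 (132 per arm) against ETA and 108 (about 54 per arm) against stripping. The nearest planning value for subjects without index-procedure data is the 3% attrition for the truncal-disease endpoint (protocol 14.1.1, SAP 6.1.1). That value reproduces: 220/(1 - 0.03) = 226.8, rounded up to the stated 227. The illustrative 20% is the phlebitis rate in the 50-patient single-arm VenaSeal study in protocol 4.1 (10 patients). Untreated and crossover shares above 3%, and the other event rates below, are assumptions.

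**Dilution.** ITT rate = true rate × (N - untreated)/N.
- 3% untreated: 0.20 × 0.97 = 19.4%.
- 5% and 10% untreated (assumed): 0.20 × 0.95 = 19.0%; 0.20 × 0.90 = 18.0%.
- In whole subjects, 3, 7 or 13 untreated of 132 give 19.5%, 18.9% or 18.0%. With 1, 3 or 5 of 54, the rates are 19.6%, 18.9% or 18.1%.

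**Unequal non-treatment, equal true risk of 20%.**
- All of the 3% in one arm, so 6% of that arm: 0.20 × 0.94 = 18.8% against 20.0%, a false gap of 1.2 points.
- 13 of 132 controls and 3 of 132 VenaSeal subjects untreated: 0.20 × 119/132 = 18.0% against 0.20 × 129/132 = 19.5%, a gap of 1.5 points.

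Depending on which arm truly has the higher risk, such a gap adds to a real difference or hides part of it.

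**Crossover.** ITT control rate = (pV × x + pC × (N - x))/N, where x controls receive VenaSeal. Assume true rates of 20% with VenaSeal and 5% with control, and N = 132:
- x = 3: (0.6 + 6.45)/132 = 5.3%; the difference falls from 15.0 to 14.7 points.
- x = 7: (1.4 + 6.25)/132 = 5.8%; 14.2 points.
- x = 13: (2.6 + 5.95)/132 = 6.5%; 13.5 points.

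**Rare device-specific events.** If 5% of VenaSeal-treated subjects had an adhesive reaction (assumed), 7 crossovers would carry 0.05 × 7 = 0.35 expected events, so often none is misplaced. One that is misplaced adds 1/132 = 0.8% to the ETA column, or 1/54 = 1.9% to the stripping column, where adhesive reactions should be zero.

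**The case against.** The case for leaving the plan alone has weight. ITT is the primary set declared in the protocol, and it preserves the randomised comparison. Neither safety endpoint is tested and the study has no primary safety endpoint (protocol 15.1), so type I error and power are untouched. Wrong-modality treatment is a major, reportable deviation, and deviations are summarised by arm (SAP 7.1.2). Disposition shows how many subjects received therapy (SAP 7.1.1). SAP 7.10 gives AE counts by relatedness to device and procedure, and a listing of all AEs. A careful reader could recover much of the missing information.

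This limits the point, and four stronger readings that a reader might infer do not follow:
- *All AE and SAE rates are biased low.* An all-subject denominator is explicit only for the crude SAE proportion. For target-limb AEs, dilution is an inference from the general call for percentages.
- *Both problems always weaken safety signals.* Crossover pulls the arms together, but unequal non-treatment can create a difference as well as hide one.
- *Causality is assigned to the wrong device.* Relatedness is recorded event by event; ITT changes only the column in which an event is tabulated.
- *The AT set can be used as it stands.* Its definition does not say where aborted procedures belong, although those subjects are followed specifically for AEs and procedure-relatedness starts at preparation (protocol 12.1.2).

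What remains is that the relatedness counts are still by study arm, a listing does not correct a summary table, and the Kaplan-Meier instruction cannot be carried out for a subject without a procedure date.

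**Conclusion.** The point holds for the two randomised studies as a descriptive weakness, probably a small one. Followed as written, the plan puts subjects who cannot have a reportable event into the crude SAE denominator, leaves them without a time origin in the survival estimate, and shows wrong-modality events under a treatment the subject did not receive. Safety is also the one area, among those where the treatment actually given matters most, that has no as-received analysis even as a sensitivity check.

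The size rests on a 20% illustrative rate and on untreated shares that the documents do not report. The shift is 0.6 points at the planned 3% and 1-2 points at an assumed 5-10%, with a false or masked between-arm gap of about 1-2 points if non-treatment is unequal. No crossover rate is available. For adhesive hypersensitivity, EGIT and EHIT, a single case is enough to change what a table shows.

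The VLU study is largely unaffected: it has one arm, and CEAP 6 subjects are enrolled only when a delivery-system component enters the body.

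**What to change.** In SAP 7.9.1.5 and 7.10:
- Define the main safety set for the randomised studies as subjects in whom an index procedure was initiated or attempted, grouped by treatment actually received.
- Keep aborted procedures in the set, under the treatment attempted, for their 30-day AE follow-up. Exclude No Procedure subjects.
- Keep the ITT tables as supporting.
- Report the numbers of no-procedure, aborted and crossover subjects by randomised arm.

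This resolves the missing day zero for No Procedure subjects. For aborted procedures, the SAP should name the date of the attempted procedure as day zero.

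The cost is SAP wording and one added set of tables; no new data are needed. The main safety table would no longer be a strictly randomised comparison, which is why ITT should stay beside it. No change is needed for the VLU study.

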| | 
• Endovenous glue induced thrombosis (EGIT) or endovenous heat induced thrombosis (EHIT)• Symptomatic deep vein thrombosis (DVT) events 
7. Additional events evaluated through 60 months (through 12 months for VenaSeal vs. Surgical Stripping Study)
 
• Symptomatic Pulmonary embolism (PE)• Serious adverse events (SAEs) 
Healthcare utilization secondary endpoints
 
8. Number and type of adjunctive treatments conducted through 12 months post-index procedure.9. Healthcare utilization related to the target limb VRD, as determined by the number of healthcare visits conducted, and other health-related resources utilized (e.g., home healthcare services) between study visits through 60 months (through 12 months for VenaSeal vs. Surgical Stripping Study).10. Procedures, tests and treatment of AEs related to the treatment modality or index procedure through 60 months (through 12 months for VenaSeal vs. Surgical Stripping Study).11. VLU Study: Healthcare utilization and routine wound care treatments between study visits through 60 months. 
Patient Experience secondary endpoints
 
12. Time to return to normal activities as reported by the patients.13. Intra-procedural and post-procedural pain at the index procedure, and pain at 7 and 30 days as reported by the patient using the numeric rating scale (NRS) with a scale of 0-10.14. Change in venous disease symptoms at 7 and 30 days, and at 6, 12, 24, 36, 48, and 60 months compared to baseline (7 and 30 days, 6 and 12 months only for VenaSeal vs. Surgical Stripping Study), as measured by the revised Venous Clinical Severity Score (rVCSS) and subject self-reporting.15. Change in AVVQ score at 30 days, and 6, 12, 24, 36, 48, and 60 months (30 days, 6 and 12 months only for VenaSeal vs. Surgical Stripping Study) compared to baseline.16. Change in EuroQoL Group 5-Dimension Self-Report Questionnaire (EQ-5D-5L) at 30 days, and 6, 12, 24, 36, 48 and 60 months (30 days, 6 and 12 months only for VenaSeal vs. Surgical Stripping Study) compared to baseline. |
|--|--|

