The VenaSeal™ closure system was developed as a non-thermal, non-tumescent and non-sclerosant (NTNTNS) alternative to other available treatment options, specifically thermal and tumescent options which require the usage of tumescent anesthesia and involve risk of thermal injury.²⁵ The VenaSeal™ system uses a medical grade adhesive to eliminate the primary source of reflux by coaptating the vein walls. Closure of the insufficient vein is accomplished through polymerization of a cyanoacrylate-based adhesive delivered via a catheter, and the resultant acute coaptation of blood flow is followed by eventual encapsulation of the blockage.

Summary of VenaSeal™ Closure System Clinical Studies

Feasibility Study

The Feasibility Study was a prospective, single center study performed in the Dominican Republic to assess safety and VenaSeal™ effectiveness to treat VRD in the GSV. Effectiveness results of the Feasibility Study indicated a 94.7% closure rate at 6 months following the index procedure. Subjects were followed for 36 months in total. There were 4 Serious Adverse Events (SAEs) reported in 3 subjects, with 1 of the 4 determined to be related to the study device or study procedure. An additional 24 Adverse Events (AEs) were reported in 17 subjects. Finally, 1 Deep Vein Thrombosis (DVT) was observed at 31 months post-treatment in a hypercoagulable subject (unknown device relationship, not related to the procedure).

eSCOPE Post-Market Study

The eSCOPE Post-Market Study was a multicenter, prospective, single arm study conducted in Europe designed to record the clinical outcomes of the CE-marked VenaSeal™ closure system for its approved indications. The primary objective was to assess the role of the VenaSeal™ system in closure of incompetent GSVs in a routine clinical setting. Effectiveness and safety (AEs) were compared to appropriate literature reports as per individual study protocols to determine if the results of the treatment of reflux disease with the VenaSeal™ system were consistent with or better than the expectations of the medical community for alternative treatments, specifically endovenous laser thermal ablation and RFA. Effectiveness results indicated a 91.4% closure rate at 6 months, declining to 88.5% closure at 36 months. At 6 months, safety analysis observed 32 AEs, one of which was an unrelated serious adverse event.

VeClose IDE Pivotal Study

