 - Endovenous glue induced thrombosis (EGIT) or endovenous heat induced thrombosis (EHIT)
 - Symptomatic deep vein thrombosis (DVT) events
7. Additional events evaluated through 60 months (through 12 months for subjects enrolled in the VenaSeal vs. Surgical Stripping Study):
 - Symptomatic pulmonary embolism (PE)
 - Serious adverse events (SAEs)

Healthcare utilization secondary endpoints

8. Number and type of adjunctive treatments conducted through 12 months post-index procedure.
9. Healthcare utilization related to the target limb VRD, as determined by the number of healthcare visits conducted, and other health-related resources utilized (e.g., home healthcare services) between study visits through 60 months (30 days, 6 and 12 months only for subjects enrolled within the VenaSeal vs. Surgical Stripping Study).
10. Procedures, tests and treatment of AEs related to the treatment modality or index procedure.
11. VLU Study: Healthcare utilization and routine wound care treatments between study visits through 60 months.

Patient Experience secondary endpoints

12. Time to return to normal activities as reported by the patients.
13. Intra-procedural and post-procedural pain at the index procedure, and 7 days and 30 days as reported by the patient using the numeric rating scale (NRS) with a scale of 0-10.
14. Change in venous disease symptoms at 7 and 30 days, and at 6, 12, 24, 36, 48, and 60 months compared to baseline (7 days, 30 days, 6 and 12 months only for subjects enrolled in the VenaSeal vs. Surgical Stripping Study), as measured by the revised Venous Clinical Severity Score (rVCSS) and subject self-reporting.

15. Change in AVVQ score at 30 days, and 6, 12, 24, 36, 48, and 60 months (30 days, 6 and 12 months only for subjects enrolled in the VenaSeal vs. Surgical Stripping Study) compared to baseline.
16. Change in EuroQoL Group 5-Dimension Self-Report Questionnaire (EQ-5D-5L) at 30 days, and 6, 12, 24, 36, 48 and 60 months (30 days, 6 and 12 months only for subjects enrolled in the VenaSeal vs. Surgical Stripping Study) compared to baseline.
17. Change in the 36-Item Short Form Health Survey (SF-36) reported by the patient at 30 days, and 6 and 12 months compared to baseline.
18. Change in the Venous Dependent Quality of Life (VenousDQoL) reported by the patient at 30 days, and 6, 12, 24, 36, 48, and 60 months (30 days, 6 and 12 months only for subjects enrolled in the VenaSeal vs. Surgical Stripping Study) compared to baseline.

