13.1. Clinical Events Committee (CEC)

A Clinical Events Committee will provide independent medical review and adjudication of AE data. The CEC will adjudicate only the safety endpoint events specified in the CEC Charter reported by the investigators. Source documents to support adjudication may be requested. Further AEs may be reviewed and adjudicated upon request of the sponsor. The CEC will follow the definitions for classifying AEs that relate to clinical safety endpoints as described in the CEC Charter.

The CEC members will be free from bias towards the study and will be independent from the study investigators, Medtronic and regulatory authorities. The committee will consist of experts (non-Medtronic employed physicians) with training or experience relevant to the study.

Events for all three Studies requiring at minimum adjudication include the following through 12 months post-index procedure:

1. Specific target limb adverse events (AEs):

- Hypersensitivity to VenaSeal™ adhesive
- Phlebitis
- Granuloma
- EGIT or EHIT

In addition, any Serious Adverse Events (SAEs) will be adjudicated through 12 months post-index procedure.

Medtronic Business Restricted

CONFIDENTIAL

056-F275, v B Clinical Investigation Plan Template

The CEC will be established and led by:

NAMSA (previously Syntactx)
[name]
[name]
[name]

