4.2.2 Additional Secondary Endpoints in the Randomized Studies

The other secondary objectives of the study are to evaluate the VenaSeal™ system in the treatment of symptomatic venous reflux in the superficial truncal veins. Specific areas of analysis include effectiveness, safety, healthcare utilization, patient experience, and treating physician experience.

Effectiveness endpoints

1. Anatomic closure of the primary target vein at 30 days, and 12, 24, 36, 48 and 60 months
2. Anatomic closure of target vein at 30 days, and 6, 12, 24, 36, 48 and 60 months
3. Technical success of each target vein immediately post-index procedure
4. Reintervention of any target vein (including primary target vein) through 60 months
5. Time to reintervention of any target vein

Safety endpoints

1. Adverse events occurring in the target limb, evaluated from index procedure through 12 months
2. Serious adverse events evaluated through 60 months (through 12 months for VenaSeal vs. Surgical Stripping Study)

Healthcare utilization endpoints

1. Number and type of adjunctive treatments conducted through 12 months post-index procedure
2. Healthcare utilization related to the target limb Venous Reflux Disease through 60 months (through 12 months for VenaSeal vs. Surgical Stripping Study)
3. Procedures, tests, and treatment of AEs related to the treatment modality or index procedure through 60 months (through 12 months for VenaSeal vs. Surgical Stripping Study)

Patient experience endpoints

1. Time to return to normal activities
2. Intra-procedural and post-procedural pain at the index procedure, and 7 days and 30 days
3. Change in venous disease symptoms at 7 and 30 days, and at 6, 12, 24, 36, 48, and 60 months compared to baseline (7 and 30 days, 6 and 12 months only for VenaSeal vs. Surgical Stripping Study)
4. Change in AVVQ score at 30 days, and 6, 12, 24, 36, 48, and 60 months (30 days, 6 and 12 months only for VenaSeal vs. Surgical Stripping Study) compared to baseline
5. Change in EuroQoL Group 5-Dimension Self-Report Questionnaire (EQ-5D-5L) at 30 days, and 6, 12, 24, 36, 48 and 60 months (30 days, 6 and 12 months only for VenaSeal vs. Surgical Stripping Study) compared to baseline
6. Change in the 36-Item Short Form Health Survey (SF-36) reported by the patient at 30 days, and 6 and 12 months compared to baseline

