The probability of experiencing an SAE through 12 months will be estimated using the Kaplan-Meier method. Day zero is the date of the index procedure. The censoring time is the time to study exit, the later of either the last contact date or the discontinuation date, or the time point for analysis, whichever comes first. The DVT and PE events will be summarized by reporting the number of events of each type and the number of patients in which they occurred. Additionally, summary statistics will report the proportion of SAEs. Numerator is the number of target limbs (or subjects) with an SAE through 12 months, denominator is the number of target limbs (or subjects).

Determination of Subjects for Analysis

The safety analysis will consist of the ITT population.

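### SAP 7.9.1.5 stops the PE and SAE endpoint analysis at 12 months against a 60-month endpoint, and the source for SAEs after month 12 is not pre-specified

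*SAP*

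**What the plan says.** Protocol 5.2.3 item 7 covers symptomatic PE and SAEs and reads "Additional events evaluated through 60 months (through 12 months for subjects enrolled in the VenaSeal vs. Surgical Stripping Study". The protocol synopsis has the same split. The SAP's own endpoint list in 4.2.2 agrees for SAEs: "Serious adverse events evaluated through 60 months (through 12 months for VenaSeal vs. Surgical Stripping Study".

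The analysis specification differs. SAP 7.9.1.5 item 2, which serves both randomised studies, groups symptomatic DVT, PE and SAEs under "Additional events evaluated through 12 months", with no exception for the ETA study. It specifies a 12-month Kaplan-Meier probability of an SAE by arm, a 12-month SAE proportion, and counts of DVT and PE.

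For the VLU study, SAP 7.9.2.4 item 2 lists the same three event types under a 60-month heading. Its method then says "The probability of experiencing an SAE through 12 months will be estimated using the Kaplan-Meier method", and the SAE proportion is also limited to 12 months. The DVT and PE counts there have no such limit.

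On the data source, both SAP sections state "CEC determination of serious adverse events will be used for reporting"; DVT and PE come from MedDRA codes. Protocol 13.1 says of the committee: "In addition, any Serious Adverse Events (SAEs) will be adjudicated through 12 months post-index procedure".

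SAP 7.10 separately promises SAE tabulation up to 60 months (12 for stripping), adverse event counts through 60 months for each arm, and 60-month tables by treatment, system organ class and preferred term. Protocol 14.3 also tabulates SAEs up to 60 months.

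**The concern.** Subjects in the ETA and VLU studies are followed for five years with an adverse event assessment at each visit. If the endpoint section is followed as written, the by-arm SAE estimate uses only the first of those years, and the PE summary in the ETA study is cut at the same point, although the protocol sets both at 60 months.

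The source is a second problem. An analyst who extends the SAE analysis to month 60 must choose between three readings: count only CEC-determined events, which are assured only to month 12; combine adjudicated and site-reported events under one label; or settle the rule once data are in hand. The trial is open-label, and protocol section 6 lists CEC-based safety reporting among its measures against bias, so this choice should not be left to the analysis stage.

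**Working it through.** The plan gives no figure to reproduce here. The check sets the provisions side by side.

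| Provision | Events | Horizon, ETA study | Horizon, VLU study |
|---|---|---|---|
| Protocol 5.2.3 item 7 | PE, SAEs | 60 months | 60 months |
| SAP 4.2.2 | SAEs | 60 months | not covered (randomised list) |
| SAP 7.9.1.5 item 2 | DVT, PE, SAEs | 12 months | not applicable |
| SAP 7.9.2.4 item 2, heading | DVT, PE, SAEs | not applicable | 60 months |
| SAP 7.9.2.4 item 2, method | SAE estimate and proportion | not applicable | 12 months |
| SAP 7.10 tabulations | SAEs, all AEs | 60 months | 60 months |
| Protocol 13.1, CEC review | SAEs | 12 months | 12 months |

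1. **Horizon, ETA study.** SAP 7.9.1.5 item 2 conflicts with protocol endpoint 7 for PE and SAEs, and with SAP 4.2.2 and 7.10 for SAEs. For the stripping study, 12 months is correct throughout.
2. **Horizon, VLU study.** The heading and the SAE method in 7.9.2.4 item 2 disagree. The PE and DVT counts do not.
3. **DVT.** The protocol places symptomatic DVT in item 6, evaluated through 12 months. The 12-month window for DVT in 7.9.1.5 agrees with that and is not part of the conflict.
4. **Source.** The SAP names CEC determination for SAEs, and the stated CEC commitment ends at month 12. No SAE source is named for months 12 to 60. PE does not depend on the CEC.
5. **Choice or slip.** Reintervention (7.9.1.4 items 4 and 5) and healthcare utilisation (7.9.1.6 items 2 and 3) carry the 60/12-month split. The SAP version history records the stripping study's reduction to 12 months but no shortening of this endpoint for the ETA study. SAP 7.12 requires a change from the protocol's methods to be justified in the study report. A drafting slip is the likelier explanation.

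Share of planned follow-up:

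- Covered by the endpoint-specific SAE analysis: 12 / 60 = 20%.
- Left to the 7.10 tabulations alone: (60 − 12) / 60 = 48 / 60 = 80%.
- Upper limit in subject-time, at planned enrolment and full retention: ETA 264 × 4 years = 1,056; VLU 125 × 4 years = 500; together 1,556 subject-years. Dropout lowers this.

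**The case against.** The strongest reply is that the 60-month information is already planned. SAP 7.10 tabulates SAEs to 60 months, counts adverse events by arm to 60 months and gives 60-month preferred-term tables on ITT, where PE would appear. Neither randomised summary is tested: 7.9.1.5 item 2 states no formal hypothesis. Protocol 14.3 asks only for descriptive statistics and makes a Kaplan-Meier display optional. The CEC window in 13.1 is a minimum, the sponsor may request further review, protocol section 6 mentions SAE adjudication without a time limit, and the CEC Charter is not among the documents.

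Much of this stands, and it rules out several stronger readings that a reader might infer:

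- **That the 60-month safety endpoint is not delivered at all.** SAP 7.10 and protocol 14.3 contradict this.
- **That there will be no SAE records after month 12.** Protocol 12.3 requires SAE reporting until follow-up ends or the subject exits. What is missing is a stated rule for which determination counts.
- **That PE in the VLU study is cut at 12 months.** It is not, and it comes from MedDRA codes.
- **That late thrombosis makes the case.** Protocol 4.1 records that "1 Deep Vein Thrombosis (DVT) was observed at 31 months post-treatment in a hypercoagulable subject", but the same text calls it unrelated to the procedure with unknown device relationship, and the protocol's own DVT endpoint is 12 months.
- **That the missed SAEs can be counted by projecting VeClose forward.** Carrying its 12 of 242 subjects with an SAE, from results including three-year follow-up, to month 60 at a constant rate ignores the extension study in the same section. That study reports no SAEs between months 36 and 60, admittedly with only 89 subjects completing the 60-month visit. The VeClose SAEs were also all assessed as unrelated to device or procedure.

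The reply does not remove the conflict in horizon or the unspecified source. The 7.10 tables name no SAE source and do not adjust for unequal follow-up, and protocol 6.2 itself expects higher attrition at 48 and 60 months. The Kaplan-Meier method already chosen for month 12 handles this; raw counts do not.

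**Conclusion.** The concern holds in a limited form. SAP 7.9.1.5 item 2 is wrong as written for PE and SAEs in the ETA study, because it contradicts the endpoint it is meant to analyse. SAP 7.9.2.4 item 2 is internally inconsistent for the SAE estimate and proportion. In both studies the SAE source for months 12 to 60 is not pre-specified.

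In size, the endpoint-specific SAE analysis covers 20% of planned follow-up in the ETA and VLU studies; the other 80% is reported only through the descriptive tabulations in 7.10. The documents support no estimate of the number of events affected. No hypothesis test, error rate or sample size is involved, and the stripping study is unaffected.

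This rests on reading 7.9.1.5 and 7.9.2.4 as the operative specification for these endpoints, and 13.1 as the full extent of committed adjudication. A CEC Charter that already extends SAE review to 60 months would close the source gap but not the conflict in horizon.

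**What to change.** - **SAP 7.9.1.5 item 2:** for symptomatic PE and SAEs, restore a horizon of 60 months, with 12 months for VenaSeal vs. Surgical Stripping. Leave DVT at 12 months, as in the protocol. Keep the 12-month SAE estimate and proportion, and add the 60-month Kaplan-Meier estimate and proportion by arm for the ETA study, with numbers at risk.
- **SAP 7.9.2.4 item 2:** add the 60-month SAE Kaplan-Meier estimate and proportion for the VLU study, so that the method matches the heading.
- **SAE source, both sections and 7.10:** state that SAEs are CEC-adjudicated through 12 months and investigator-reported afterwards unless adjudicated. Show the two sources separately and use the same rule in the 7.10 tables.
- **Cross-check:** align 4.2.2, 7.9.1.5, 7.9.2.4, 7.10 and the CEC scope in protocol 13.1.

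The cost is SAP wording and one extra time point per table. The data are already collected through month 60, and no further adjudication is needed if later events are labelled by source.
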